## 12.4 Interim analysis

A sponsor blinded interim analysis focused on the primary endpoint after 33% of the officers have completed participation in the study (22 in each group). The independent programmer will prepare the dataset using a pre-prepared SAS code and will freeze them for the interim analysis. To ensure the double blinding of the study the subjects will not be presented in the assigned groups. The blinded statistician will estimate the overall proportion of PTS positive subjects in each group.

With 33% information, the trial would be stopped for futility if the interim z-value  $\leq 0.5233$  ( $p=0.60$  2-sided) corresponding to a conditional power less than 10%. This design would provide 79.4% overall power (i.e. the probability of passing futility and reaching  $p<0.025$  for the comparison in the final analysis would be 79.4%).

Based on interim analysis the following actions may be taken:

- Stop the trial for futility
- Continue the trial as planned.

Early stopping rule related to serious adverse events: In the event of a serious adverse event, DSMB will evaluate the association of the serious adverse events with the study arm, break the blind if needed, and if found to be associated with treatment, DSMB will consider the study for revision or stopping.

***Serious feasibility or design difficulties.*** If one year after the start of the trial, <50% of the planned accrual goals are met, DSM and study team will discuss difficulties in recruitment. Amount of remuneration will be revised, if needed. If there are not enough officers meeting inclusion/exclusion criteria, then the criteria will be revised without impacting study objectives. If there are recruitment difficulties, the DSM will discuss with the PI and research team what are the main reasons for these difficulties and will identify ways to deal with them. For example, if there are not enough police officers identified with a TTS  $\geq 10$ dB, then the study inclusion criteria will be revised to include members of the Bomb squad. In order to preserve the balanced design and group representation, a stratified randomization strategy will be employed. If there are difficulties in recruitment related to length of

audiometric testing pre- and post-shooting, then the DSM and research team will discuss using OAE testing.

For this study, we have approximately 800 officers from Akron and Summit County, not including additional local police departments from which to screen and recruit, understanding a large percentage of the population may already present with significant NIHL, thus, may not meet the eligibility criteria. In a previous study by the investigators, 62-85% of police officers presented with evidence of NIHL (62.5% of canine police handlers and 85.7% of non-canine police handlers), therefore, we need a significantly larger sample size to recruit subjects that meet our eligibility criteria. We estimate that each year we will have at least 60 officers screened within 1 hour of shooting each year. If the rate of TTS after 1 hour of shooting is that of the study from Blioskas et al, we estimate that 48 officers will qualify to undergo randomization each year. If 70% of them consent to be randomized there will be 34 officers enrolled and completing the trial each year. Based on these estimates, we will be able to meet our accrual goals and complete the study with a sample size of 132 officers in approximately 4 years.

## **12.5 Pharmacogenetic analysis plan**

This analysis will be performed at the end of the trial by Gateway Biotechnology. To identify genetic variants with ZNS protection against hearing loss, we will first use univariate logistic regression analyses to identify potential confounding variables: sex, age, Z-scores of drug concentration, Z-scores of noise intensity and duration, and Z-scores of hearing functions measured immediately following range shooting. Single-marker allelic association analyses will be conducted on the two imputed data sets in PLINK v1.07. The data will be analyzed with a logistic regression model on the additive continuous dosage of minor alleles from 0 to 2 to account for uncertainty of imputation. We will combine association results in the two cohorts by performing a genome-wide inverse-variance weighting meta-analysis using PLINK v1.07, and assuming a fixed-effect model. Functional annotation of top-associated markers will be performed with R package NCBI2R 1.4.6 (<http://CRAN.Rproject.org/package=NCBI2R>), and key regional association plots of meta-analyzed results will be generated. To confirm whether these variants are specific to ZNS response, we will apply CEP SKAT to analyze genetic associations based on Z-scores of audiogram average threshold shifts and DPOAE amplitudes. All genetic variants, including both common and rare variants, will be included in this association study. Age, gender, drug concentration, and noise duration and intensity will be adjusted for the analysis. The analysis will also be performed using hearing data collected two to four weeks after range shooting. The only differences will be a) using the Z scores of ECochG AP amplitude, latency, and width as well as WIN score, and b) using average audiogram threshold shifts and DPOAE amplitudes at 30 days (+/- 3 days) post-treatment. To control for confounding effects, these models will be adjusted for age, gender, drug concentration, and noise duration and intensity. Finally, the control and ZNS-treated comparisons will be performed using post-hoc comparisons with a Bonferroni adjustment for multiple comparisons of any ZNS versus none.

Statistical analyses will be performed using the CEP-SKAT method in R language, and the statistical software SAS version 9.4 for Windows will be used for additional analysis.

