**Delay of ARHL in patients taking CCBs.**

In our preliminary study, a total of 35 white female patients have completed their first visit, with 26 of them using amlodipine (74%) for more than one year. We compared this CCB group with two control cohorts, also of white females: control 1 group (Con 1) from the Rochester, NY, area (447 participants) and control 2 group (Con 2) from the St. Louis, MO, area (55 participants) (Fig. 1).

Since ARHL starts at higher frequencies in the cochlea, we divided audiograms into three pure tone averages (PTA): averages of 0.25, 0.5, and 1 kHz (PTAL); averages of 2 and 4 kHz (PTAH24); and averages of 2, 4, and 8 kHz (PTAH248). The means for the CCB group were: PTAL (15.1 dB HL), PTAH24 (20.7 dB HL), and PTAH248 (24.0 dB HL), and the means for the control 1 group were: PTAL (20.1 dB HL), PTAH24 (30.7 dB HL), and PTAH248 (35.2 dB HL).

Since there were no data for 8 kHz for the control 2 group, the means for this group were PTAL (20.7, dB HL) and PTAH24 (29.3 dB HL). The two-tailed unequal variance t-test showed a significant difference between the CCB and the control 1 group for PTAL ( $p = 0.00067$ ), PTAH24 ( $p = 0.00001$ ), and PTAH248 ( $p = 0.00021$ ), and a significant difference between the CCB and control 2 groups for PTAL ( $p = 0.02777$ ) and PTAH24 ( $p = 0.00959$ ). To correct for possible influences from both age and the three cohort sites, we used multivariate regression models with the Bonferroni correction method (Table 1, 2 and 3 for PTAL, PTAH24 and PTAH248, respectively). No significant difference was observed for PTAL between the CCB and control 1 or 2 groups (Table 1), or

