### **3.3 Inclusion of Women and Minorities**

Both men and women and members of all races and ethnic groups are eligible for this trial.

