6.2 Demographics Characteristics

Demographic characteristics will be summarized descriptively by treatment group for the Safety Sample Set, including:

- Age (years) at time of consent
- Sex
- Ethnicity
- Race

Demographics characteristics will be listed.

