7.1.3 Pharmacogenetics analysis plan

This analysis will be performed at the end of the trial by Gateway Biotechnology. To identify genetic variants associated with ZNS protection against hearing loss, we will utilize genetic data collected from saliva samples to conduct a genetic association study. Variables including : sex, age, normalized values (Z-scores) of drug plasma concentration, Z-scores of noise intensity and duration, and Z-scores of hearing functions measured immediately following range shooting will be used in the analysis. Single-marker allelic association analyses will be conducted using PLINK v1.07. The data will be analyzed with a logistic regression model on the additive continuous dosage of minor alleles from 0 to 2 to account for uncertainty of imputation. We will combine association results in the two cohorts by performing a genome-wide inverse-variance weighting meta-analysis using PLINK v1.07, and assuming a fixed-effect model. Functional annotation of top-associated markers will be performed with R package NCBI2R 1.4.6 (<http://CRAN.Rproject.org/package=NCBI2R>), and key regional association plots of meta-analyzed results will be generated. To confirm whether these variants are specific to ZNS response, we will apply CEP SKAT to analyze genetic associations based on Z-scores of audiogram average threshold shifts and DPOAE amplitudes. All genetic variants, including both common and rare variants, will be included in this association study. Age, gender, drug concentration, and noise duration and intensity will be adjusted for the analysis. The analysis will also be performed using hearing data collected two to four weeks after range shooting. The only

differences will be a) using the Z scores of ECochG AP amplitude, latency, and width as well as WIN score, and b) using average audiogram threshold shifts and DPOAE amplitudes at 30 days (+/- 3 days) post-treatment. To control for confounding effects, these models will be adjusted for age, gender, and noise duration and intensity. Finally, the control and ZNS-treated comparisons will be performed using post-hoc comparisons with a Bonferroni adjustment for multiple comparison testing. Statistical analyses will be performed using the CEP-SKAT method in R language, and the statistical software SAS version 9.4 for Windows will be used for additional analysis.

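### The pharmacogenetic marker models have no genetic-ancestry term, so associations from pooled or within-arm scans can be confounded if hearing outcome and allele frequency both differ by ancestry

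*Protocol*

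**What the plan says.** Protocol 12.5 names its covariates in three places.

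- **Confounder screen before the single-marker analysis:** "we will first use univariate logistic regression analyses to identify potential confounding variables: sex, age, Z-scores of drug concentration". The list continues with noise intensity and duration and with hearing measured just after shooting.
- **CEP-SKAT models:** "Age, gender, drug concentration, and noise duration and intensity will be adjusted for the analysis".
- **30-day models:** "To control for confounding effects, these models will be adjusted for age, gender, drug concentration, and noise duration and intensity".

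SAP 7.1.3 follows the same plan. Its opening list of variables is worded openly. Its last adjustment sentence is closed and drops drug concentration: "To control for confounding effects, these models will be adjusted for age, gender, and noise duration and intensity".

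On who can enter, Protocol 3.3 says: "Both men and women and members of all races and ethnic groups are eligible for this trial". Protocol 1.4 says that the approaches of the preliminary age-related hearing loss study will be applied here. In that study "a total of 35 white female patients have completed their first visit", and of the comparison groups it says: "We compared this CCB group with two control cohorts, also of white females".

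Race and ethnicity are recorded, but their stated use is descriptive. SAP 6.2 introduces the list that contains them with: "Demographic characteristics will be summarized descriptively by treatment group for the Safety Sample Set, including".

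The status of the aim differs between sections. A pharmacogenetic link is part of the secondary objectives in Protocol 2.2 and SAP 2.2.2, while SAP 3.4 places the DNA analysis under exploratory analysis.

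**The concern.** A marker-outcome model compares people by genotype, and genotype is not randomised. If two ancestry groups differ both in how often they carry an allele and in how often they show a threshold shift, a model without ancestry credits the outcome difference to the allele. Both plans say that they adjust in order to control confounding, yet they leave out this confounder, which is specific to genetic association. The preliminary work limited it by restricting to one racial group, and nothing replaces that restriction here.

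Both plans annotate and plot the top-ranked markers from a scan of common and rare variants. Where the two conditions hold, ancestry-differentiated markers are favoured in that ranking. What is at stake is the pharmacogenetic aim only: a reported marker could be a proxy for ancestry.

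**Working it through.** **Plan's own figure.** The pharmacogenetic plan states no power, error rate or significance threshold, so there is nothing to reproduce.

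**Inputs from the documents.** 132 officers, 66 per arm; planned PTS proportions 50% on placebo and 25% on ZNS (Protocol 12.3, SAP 2.7).

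**Assumed inputs, because the documents give none.** Two ancestry groups; minority share s; PTS risk p0 in the majority and p1 in the minority; allele frequency f0 and f1; a marker with no effect within either group.

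**Formula for the unadjusted additive (trend) test.** G is the allele count, Y is PTS, and m is the overall PTS risk.

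- Cov(G,Y) = s(1−s) × 2(f1−f0) × (p1−p0)
- Var(Y) = m(1−m)
- Var(G) = (1−s)·2f0(1−f0) + s·2f1(1−f1) + 4s(1−s)(f1−f0)²
- Expected |z|: λ = √N × |Cov| / √(Var(Y)·Var(G))
- False-positive rate at two-sided 5% ≈ Φ(−1.96+λ) + Φ(−1.96−λ)

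**Scenario A worked through.** s = 0.15, PTS 42% v 22%, allele frequency 0.10 v 0.60, N = 132.

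- |Cov| = 0.1275 × 1.0 × 0.20 = 0.0255
- m = 0.85×0.42 + 0.15×0.22 = 0.39; Var(Y) = 0.39×0.61 = 0.2379
- Var(G) = 0.153 + 0.072 + 0.1275 = 0.3525
- λ = 11.49 × 0.0255/√(0.2379×0.3525) = 11.49 × 0.0881 = 1.01
- Rate ≈ Φ(−0.95) + Φ(−2.97) = 17%

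**All scenarios.** The formula is a large-sample approximation and runs slightly above simulation. Simulations used 20,000 or more replicates.

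| Scenario | N | λ | Formula | Simulated, no ancestry term | Simulated, ancestry term |
|---|---|---|---|---|---|
| A: share 15%, PTS 42% v 22%, allele 0.10 v 0.60 | 132 | 1.01 | 17% | 16.0% | 4.7% |
| B: as A, share 25% | 132 | 1.34 | 27% | 26.4% | 4.4% |
| C: share 15%, PTS 40% v 30%, allele 0.10 v 0.30 | 132 | 0.25 | 5.7% | 5.6% | 5.0% |
| D: as A and B, one arm | 66 | 0.72-0.95 | 11-16% | 9-14% | not run |
| E: one arm, PTS 28% v 15%, allele 0.10 v 0.60, share 15-25% | 66 | 0.52-0.69 | 8-11% | 6-8% | not run |
| F: equal PTS risk in both groups | 132 | 0 | 5% | 4.8-5.1% | 4.8-5.0% |

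Larger assumed gaps give larger figures: PTS 45% v 15% with allele frequency 0.10 v 0.60 and a 25% share gives 53% unadjusted and 3.7% adjusted. That shows how far the answer depends on inputs that the documents do not supply.

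**Pooling two cohorts.** If the two cohorts in the planned fixed-effect meta-analysis are the arms, the bias has the same direction in both and does not cancel. With placebo PTS 55% v 30% by ancestry, halved on ZNS, and allele frequency 0.10 v 0.60, the pooled rate is 15-25% unadjusted and about 4.6% adjusted.

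**Comparing marker slopes between arms.** With 66 per arm, the inputs of A and B and no true interaction, the false-positive rate is about 4-6%. Ancestry is balanced on average, so its effect on prognosis appears in both slopes and largely drops out.

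**Room for extra covariates.** Expected PTS events are 66×0.25 = 16.5 on ZNS and 66×0.50 + 16.5 = 49.5 overall. The marker, age, gender, drug concentration, noise duration and noise intensity already use six terms, or 16.5/6 = 2.75 events per term in a ZNS-only logistic model. Two components give 16.5/8 = 2.1; five give 16.5/11 = 1.5.

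**The case against.** The strongest reply is that the harm is conditional and the analysis is exploratory. Both parts stand. Harm needs outcome and allele frequency both to differ by ancestry, and no section says that PTS does. The 15-26% range needs a 20-point PTS gap with a 50-point allele-frequency gap, which need not describe a typical marker. SAP 3.4 does class the work as exploratory, although both documents also write it into the secondary objectives.

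A second reply is that the plan ends with comparisons of control and ZNS-treated officers, which randomisation protects. That stands for a true between-arm comparison of marker effects. But neither document writes a marker-by-treatment term, and the single-marker and CEP-SKAT steps are marker-outcome associations. The Bonferroni step at the end deals with multiplicity, not with bias.

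A third reply is that the adjusted 4-5% conditions on the true simulated ancestry label. Estimated components or self-reported race may correct less completely, and CEP-SKAT was not simulated. That stands as a limit on the figures. It does not justify leaving the term out.

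A fourth is that more basic gaps come first: the two cohorts and the two imputed data sets are undefined, and the scan has no significance threshold. That is fair. An ancestry term does not by itself make a scan of 132 people interpretable.

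**Conclusion.** The omission is in both documents and nothing elsewhere in them repairs it. Marker associations from pooled or within-arm scans are open to confounding by ancestry if hearing outcome and allele frequency both differ by ancestry. The table shows the size, from nominal when outcome does not differ up to about a quarter of null markers at nominal 5% in scenario B. Every entry rests on an assumed ancestry mix, assumed outcome rates and assumed allele frequencies.

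A reader might infer two stronger things that the documents do not support. One is that officers of all races will be enrolled and the results will therefore be confounded: Protocol 3.3 speaks of eligibility, and the actual mix is not given. The other is that any claim of ZNS response would be spurious: a between-arm comparison of marker effects is largely protected.

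The primary PTS comparison does not use these models and is unaffected. The point is minor and limited to the pharmacogenetic analysis.

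**What to change.** In Protocol 12.5 and SAP 7.1.3:

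1. Pre-specify a small fixed number of leading genotype principal components, for example 2-3, as covariates in the PLINK logistic models and in the CEP-SKAT null model. Use fewer in any ZNS-only logistic model, given the 16-17 PTS events expected there.
2. If components cannot be computed, use the recorded race and ethnicity (SAP 6.2).
3. Report the genomic inflation factor.
4. Base any claim of ZNS response on a marker-by-treatment comparison, and write that term into the plan.
5. Reconcile the two documents on whether drug concentration is a covariate in the 30-day models.

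The cost is wording in two sections. No new data are needed, because DNA, race and ethnicity are already to be collected. The downside is a few degrees of freedom and some loss of stability in sparse logistic models, which is why the number of components should be small and fixed before the genetic data are analysed.

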## **APPENDIX A: Definitions for Adverse Event Reporting**

### **A. Adverse Events (AEs)**

As defined in 21 CFR 312.32:

**Definition:** any untoward medical occurrence associated with the use of a drug in humans, whether or not considered drug-related.

**Grading:** the descriptions and grading scales that should be used are those provided by the Department of Health and Human Services' Office for Human Research Protections (OHRP). A copy of this guidance can be found on OHRP's website:

<http://www.hhs.gov/ohrp/policy/advevntguid.html>

**Attribution (relatedness), Expectedness, and Seriousness:** the definitions for the terms listed that should be used are those provided by the Department of Health and Human Services' Office for Human Research Protections (OHRP). A copy of this guidance can be found on OHRP's website:

<http://www.hhs.gov/ohrp/policy/advevntguid.html>

### **B. Suspected Adverse Reaction (SAR)**

As defined in 21 CFR 312.32:

**Definition:** any adverse event for which there is a reasonable possibility that the drug caused the adverse event. "Reasonable possibility" means there is evidence to suggest a causal relationship between the drug and the adverse event. "Suspected adverse reaction" implies a lesser degree of certainty about causality than adverse reaction, which means any adverse event caused by a drug.

### **C. Life-Threatening Adverse Event / Life Threatening Suspected Adverse Reaction**

As defined in 21 CFR 312.32:

**Definition:** any adverse drug event or suspected adverse reaction is considered "life-threatening" if, in the view of the investigator, its occurrence places the patient at immediate risk of death. It does not include an adverse event or suspected adverse reaction that, had it occurred in a more severe form, might have caused death.

### **D. Serious Adverse Event (SAE) or Serious Suspected Adverse Reaction**

As defined in 21 CFR 312.32:

**Definition:** an adverse event or suspected adverse reaction is considered "serious" if, in the view of the investigator, it results in any of the following outcomes:

- Death

- A life-threatening adverse event
- Inpatient hospitalization or prolongation of existing hospitalization
- A persistent or significant incapacity or substantial disruption of the ability to conduct normal life functions
- A congenital anomaly/birth defect
- Any other important medical event that does not fit the criteria above but, based upon appropriate medical judgment, may jeopardize the subject and may require medical or surgical intervention to prevent one of the outcomes listed above

#### **E. Protocol Exceptions**

**Definition:** A planned change in the conduct of the research for one participant.

#### **F. Deviation**

**Definition:** Any alteration or modification to the IRB-approved research without prospective IRB approval. The term “research” encompasses all IRB-approved materials and documents including the detailed protocol, IRB application, consent form, recruitment materials, questionnaires/data collection forms, and any other information relating to the research study.

A minor or administrative deviation is one that does not have the potential to negatively impact the rights, safety, or welfare of participants or others or the scientific validity of the study.

A major deviation is one that does have the potential to negatively impact the rights, safety, or welfare of participants or others or the scientific validity of the study.

## APPENDIX B: Reporting Timelines

Event	HRPO	FDA
Serious AND unexpected suspected adverse reaction		Report no later than 15 calendar days after it is determined that the information qualifies for reporting
Unexpected fatal or life-threatening suspected adverse reaction		Report no later than 7 calendar days after initial receipt of the information
Unanticipated problem involving risk to participants or others	Report within 10 working days. If the event results in the death of a participant enrolled at WU/BJH/SLCH, report within 1 working day.	
Major deviation	Report within 10 working days. If the event results in the death of a participant enrolled at WU/BJH/SLCH, report within 1 working day.	
A series of minor deviations that are being reported as a continuing noncompliance	Report within 10 working days.	
Protocol exception	Approval must be obtained prior to implementing the change	
Clinically important increase in the rate of a serious suspected adverse reaction of that list in the protocol or IB		Report no later than 15 calendar days after it is determined that the information qualifies for reporting
Complaints	If the complaint reveals an unanticipated problem involving risks to participants or others OR noncompliance, report within 10 working days. If the event results in the death of a participant enrolled at WU/BJH/SLCH, report within 1 working day. Otherwise, report at the time of continuing review.	
Breach of confidentiality	Within 10 working days.	
Incarceration	If withdrawing the participant poses a safety issue, report within 10 working days.  If withdrawing the participant does not represent a safety issue and the patient will be withdrawn, report at continuing review.	

Event	HRPO	FDA
Adverse event or SAE that does not require expedited reporting	If they do not meet the definition of an unanticipated problem involving risks to participants or others, report summary information at the time of continuing review	The most current toxicity table from the DSM report is provided to the FDA with the IND's annual report.
Minor deviation	Report summary information at the time of continuing review.	
Complaints	If the complaint reveals an unanticipated problem involving risks to participants or others OR noncompliance, report within 10 working days. If the event results in the death of a participant enrolled at WU/BJH/SLCH, report within 1 working day. Otherwise, report at the time of continuing review.	
Incarceration	If withdrawing the participant poses a safety issue, report within 10 working days.  If withdrawing the participant does not represent a safety issue and the patient will be withdrawn, report at continuing review.	

Event	WU (Coordinating Center)	Local IRB	FDA
Serious AND unexpected suspected adverse reaction	Report no later than 11 calendar days after it is determined that the information qualifies for reporting.	Report all applicable events to local IRB according to local institutional guidelines.	The research team at Washington University is responsible for reporting all applicable events to the FDA as needed.
Unexpected fatal or life-threatening suspected adverse reaction	Report no later than 4 calendar days after initial receipt of the information.		
Unanticipated problem involving risk to participants or others	Report no later than 4 calendar days after initial receipt of the information.		
Adverse event or SAE that does not require expedited reporting	As per routine data entry expectations		
Protocol exception	Approval must be obtained prior to implementing the change.		

